The START-CKD study is designed to describe the benefits and potential risks of a new treatment strategy using a fixed dose of darbepoetin alfa in subjects with chronic kidney disease and not on dialysis (ND-CKD). Subjects will be randomly allocated to treatment with a fixed dose of darbepoetin alfa or to treatment with darbepoetin alfa using a hemoglobin (Hb)-based titration strategy, which has been the conventional dosing strategy. This study aims to estimate the incidence of red blood cell (RBC) transfusions (administered as deemed clinically necessary) in each group and the difference in incidence of RBC transfusions between the 2 groups. In addition, multiple aspects, such as cumulative darbepoetin alfa dose, total number of units of transfusions, Hb concentration, Hb-related parameters (eg, Hb variability, excursions, rate of change), and adverse (eg, cardiovascular) events, will also be considered in order to determine a preferred dosing regimen.

Protocol Synopsis

Title: START-CKD: Strategies Using Darbepoetin alfa to Avoid Transfusions in Chronic Kidney Disease

Study Phase: 3

Indication: Management of anemia in chronic kidney disease patients not on dialysis.

Primary Objective: To evaluate the incidence of RBC transfusions in ND-CKD subjects using either a Hb-based titration algorithm or a weight-based dose that will not be titrated (fixed dose), and to evaluate the difference in the incidence of RBC transfusions between the 2 groups.

Secondary Objective(s)

To summarize the following for each dosing strategy:

- Transfusion burden
- Time to first RBC transfusion
- Achieved Hb concentration
- Cumulative dose of darbepoetin alfa

To describe the difference in each of the above between the two dosing strategies.

Safety Objective: To describe the safety profile of darbepoetin alfa, including adverse events and the occurrence of adjudicated clinical events of interest.

Exploratory Objective(s)

To describe with each dosing strategy:

- Dose and Hb-related parameters
- Initial Hb response and resulting dose and achieved Hb
- Duration of hospitalization
- Allosensitization over time

Hypotheses: The incidence of RBC transfusions in each treatment group (Hb-based titration group and fixed dose group) and their difference will be estimated, and no formal hypothesis will be tested. The width of the 95% confidence interval (CI) of the transfusion incidence rate is expected to be < 10% (ie, \pm 5% around the point estimate) in each group and the width of the 95% CI of the difference in transfusion incidence rates is expected to be < 14% (ie, \pm 7% around the point estimate). The efficacy and safety of each treatment group will be described, as these aspects will assist in the determination of a preferred dosing regimen.

Primary Endpoint: Receipt of 1 or more RBC transfusion

Secondary Endpoint(s)

- Total number of units of RBC transfused
- Time to first RBC transfusion
- Average achieved Hb concentration while receiving investigational product
- Cumulative dose of darbepoetin alfa

Safety Endpoint(s)

- Time to major clinical events:
 - Composite of all-cause mortality and the occurrence of major cardiovascular events (stroke, myocardial infarction, and decompensated heart failure)
 - Composite of all-cause mortality, stroke or myocardial infarction, ie, major adverse cardiovascular events (MACE)
 - All-cause mortality
 - Cardiovascular mortality
 - Stroke
 - Myocardial infarction
 - Decompensated heart failure
 - Thromboembolic events
 - Vascular access thrombosis
- Adverse events
- Blood pressure and pulse
- Anti-erythropoietic protein antibodies

Exploratory Endpoint(s)

- Darbepoetin alfa dose received at each study visit
- Hb concentration at each study visit
- Hb concentration change from baseline at each study visit
- Time to first Hb concentration ≥ 10.0 g/dL
- Proportion of Hb measurements ≥ 10.0 g/dL
- Hb rate of change in a 4 week interval at each study visit
- Hb variability, defined as the intrasubject standard deviation over a 6 month rolling window
- Initial Hb response, defined as the change of Hb concentration from baseline at week 5
- Darbepoetin alfa dose over time by initial Hb response
- Hb over time by initial Hb response
- Number of days hospitalized
- Anti-human leukocyte antigen (HLA) antibodies

Study Design: This is a phase 3, multicenter, randomized, double-blind, parallel group study. Anemic, ND-CKD subjects, without recent ESA use, will be randomized to 1 of 2 dosing strategies. In the Hb-based titration group, darbepoetin alfa doses will be titrated to maintain Hb \geq 10.0 g/dL. In the other group, subjects will receive a fixed dose of darbepoetin alfa. All subjects will receive investigational product (IP) as a subcutaneous injection every 4 weeks (Q4W). Treatment group, darbepoetin alfa doses, and protocol specified Hb concentrations will be blinded to the investigator, subjects and study team. Subjects will be followed for approximately 2 years from the date of randomization.

Sample Size: A total of approximately 750 subjects (approximately 375 per treatment group) will be randomized.

Summary of Subject Eligibility Criteria

Anemic ND-CKD subjects:

- Age 18 or older
- Two Hb concentrations < 10.0 g/dL at least 2 weeks apart
- **Not currently receiving dialysis with an estimated** glomerular filtration rate of < 45.0 mL/min/1.73m² **during screening**
- Iron replete, defined as a transferrin saturation (TSAT) $\geq 20\%$ and a ferritin ≥ 100 ng/mL
- Clinically stable by the investigator

Who have not:

- Received erythropoiesis stimulating agents (ESAs) within 4 weeks of screening
- Received an RBC transfusion within 8 weeks of screening
- Received intravenous iron or had changes to oral iron therapy within 4 weeks of screening

For a full list of eligibility criteria, please refer to [Section 4](#).

Amgen Investigational Product Dosage and Administration

Investigational product (darbepoetin alfa or placebo) will be administered subcutaneously every 4 weeks. Darbepoetin alfa will be supplied as a clear, colorless, sterile protein solution in single use prefilled syringes (PFS) at concentrations of 10, 20, 30, 40, 50, 60, 80, 100, 150, 200 and 300 μ g. Placebo will be provided in similar PFS as a clear, colorless, sterile solution.

The protocol specified doses (PSD) for use in this study are 10, 20, 30, 40, 50, 60, 80, 100, 120, 150, 200, 250, and 300 μ g.

Every 4 weeks a protocol specified Hb will be measured using an **modified** Hb point of care (POC) device and the results will be blinded. The codes provided by the **modified** Hb POC device and the mean systolic blood pressure (SBP) will be entered into the interactive voice response/interactive web response (IVR/IWR) system at each dosing visit. The mean SBP obtained from additional blood pressure monitoring visits will also be entered into the IVR/IWR system.

In both dosing groups, the dose of investigational product will be withheld if the subject's mean SBP is ≥ 160 mmHg for three consecutive visits (including blood pressure monitoring visits). Investigational product will be restarted at the dosing visit when the mean SBP is ≤ 140 mmHg.

Subjects randomized to the Hb-based titration group will receive an initial dose of darbepoetin alfa of 0.45 μ g/kg, based on the subject's screening weight, rounded down to the next lower PFS strength. Subsequently, the dose of darbepoetin alfa will be titrated based on the Hb concentration at the current visit and rate of rise (ROR) as outlined in the table below. The Hb ROR will be determined by the protocol specified Hb concentrations obtained from the previous dose to the current dose. An IVR/IWR system will be used to determine and assign each dose. Subjects may be assigned 2 injections to ensure they receive the dose assigned for that visit.

Dosing Algorithm for Hb-based Titration Group

Hb (g/dL)	Hb ROR (g/dL/4W)		
	≤ 1.0	> 1.0 and ≤ 2.0	> 2.0
<10.0	↑ to next higher PSD ^a	Maintain	↓ to next lower PSD ^b
10.0-10.5	Maintain	↓ to next lower PSD ^b	↓ to next lower PSD ^b
>10.5 -11.0	↓ to next lower PSD ^b	↓ to next lower PSD ^b	Placebo ^c
>11.0	Placebo ^c	Placebo ^c	Placebo ^c

^a Subjects receiving 300 µg who require a dose increase will continue to receive 300 µg

^b Subjects receiving 10 µg who require a dose reduction will receive placebo

^c Restart darbepoetin alfa when Hb < 10.0 g/dL, at next lower PSD

Subjects randomized to the fixed dose group will receive a fixed dose of darbepoetin alfa throughout the study of 0.45 µg/kg, based on the subject's screening weight, rounded down to the next lower PFS strength. The same dose of darbepoetin alfa will then be administered Q4W for the duration of the study, with 1 exception: if the Hb is > 12.0 g/dL, the darbepoetin alfa dose will be withheld and placebo will be administered until the Hb falls below 10.0 g/dL, at which time the darbepoetin alfa dose will be restarted. In order to maintain the blind when a subject in the Hb-based titration group is assigned 2 injections of investigational product, subjects in the fixed dose group will be assigned at random to receive 2 injections of investigational product.

Throughout the study, investigators should provide adequate supportive care. It is recommended that iron be administered to ensure TSAT levels of ≥ 20% and serum ferritin ≥ 100 ng/mL and blood pressure be monitored and managed as appropriate, such as to target a SBP < 130 mmHg and a diastolic blood pressure (DBP) < 80 mmHg. Subjects should not receive any other ESAs while receiving investigational product during the study.

Procedures

Informed consent will be obtained prior to the execution of any study procedures. Subject visits and assessments will occur from the time of screening through the end of study. At the conclusion of the screening period, eligible subjects will be randomized in a 1:1 ratio to 1 of 2 dosing strategies:

- Hb-based titration group: Darbepoetin alfa titrated to maintain Hb ≥ 10.0 g/dL
- Fixed dose group: Weight-based dose of darbepoetin alfa that will not be titrated

Randomization will be stratified by RBC transfusion received within 12 months prior to randomization (yes/no) and site practice setting (nephrology/non-nephrology).

Assessments during the study visits may include:

- Recording of transfusions, adverse events, concomitant medications, hospitalizations and collection of study endpoint data for adjudication
- Physical assessments (eg, blood pressure)
- Collection of laboratory samples for evaluation of blood chemistry, hematology and iron status
- Collection of blood samples for biomarkers

Subjects ending investigational product prior to week 97 will be asked to complete scheduled visits and study procedures. At a minimum, subjects must be followed for the collection of RBC transfusions and endpoint data for adjudication.

RBC transfusions should be performed as deemed necessary by the treating physician and criteria are not stipulated by this study protocol. Information regarding the context surrounding RBC transfusions will be collected throughout the study including units of RBCs transfused, the transfusion setting (eg, dialysis center, intensive care unit, emergency department) and clinical

events (eg, bleeding, surgery). This information will be reviewed by an independent Clinical Endpoint Committee (CEC).

Events of death, myocardial infarction, stroke, decompensated heart failure and thromboembolism, including vascular access thrombosis, will also be collected from randomization through the end of the study and adjudicated in a blinded fashion by the independent CEC.

Adverse events (AEs) will be collected from the time of randomization through 4 weeks following the last dose of investigational product. Serious adverse events will be collected from the date of consent. Any serious adverse events with a fatal outcome (regardless of possible relationship to investigational product) occurring through the end of the subject's participation on the study are to be reported to Amgen.

For a full list of study procedures, including the timing of each procedure, please refer to [Section 7](#) and [Appendix A](#).

Statistical Considerations

Subjects who receive at least 1 dose of investigational product will be included in the primary analysis. The evaluation period will begin at the date of randomization and subjects will be censored at the last administration of investigational product plus 3 months or end of study, whichever is earlier (on-treatment approach).

For the primary endpoint, the proportion of subjects in each treatment group receiving at least 1 RBC transfusion during the evaluation period will be presented with 2-sided 95% CIs. The difference in proportions between treatment groups and the relative risk ratio will be described with 2-sided 95% CIs. Confidence intervals will be derived using normal approximation. The primary analysis will be repeated by subgroups of interest.

As a sensitivity analysis, the primary analysis will be repeated using all randomized subjects with the evaluation period beginning at the date of randomization and subjects will be censored at the end of study (on-study approach).

Sensitivity analyses will also be performed to assess the impact of potential differential follow-up on the primary endpoint. Exposure-adjusted subject incidence of receiving at least 1 RBC transfusion will be calculated with 95% CI using Chi-square approximation to the Poisson distribution for both on-treatment and on-study approaches.

For the analyses of the secondary endpoints: total number of units of RBC transfused per subject will be summarized for each treatment group. Time to first RBC transfusion using both on-treatment and on-study approaches will be described for each treatment group. Average achieved Hb concentration while receiving investigational product will be analyzed as average Hb using the area under the curve (AUC) method. Cumulative doses of darbepoetin alfa adjusted for investigational product exposure time will also be described.

[figure not shown]
Safety endpoints will include the descriptive summary of the time to adjudicated event endpoint by treatment group, using Kaplan-Meier curves, Kaplan-Meier percentiles, the number of subjects censored, and the number of subjects with events. Subject incidence of adverse events will be tabulated by system organ class, high level group term, and preferred term by treatment group. Adverse events of interest will be tabulated by treatment group. Subgroup analyses will be presented for all adverse events.

An independent Data Monitoring Committee (DMC) will review unblinded study data on a regular basis throughout the duration of the study. The DMC may recommend modifying or stopping the study, or suspending enrollment. This recommendation can be based on any safety concerns, lack of efficacy/futility, or preponderance of early evidence of efficacy. The DMC will conduct an interim analysis, which will occur when approximately 33% of subjects have completed 12 months of planned study follow-up.

For a full description of statistical analysis methods, please refer to [Section 10](#).

Sponsor: Amgen Inc.

Study Design and Treatment Schema

Study Glossary

Abbreviation or Term	Definition/Explanation
AE	Adverse Event
AUC	Area Under the Curve
CBC	Complete Blood Count
CEC	Clinical Endpoint Committee
CHOIR	Correction of Hemoglobin and Outcomes in Renal Insufficiency
CI	Confidence Interval
CKD	Chronic Kidney Disease
CRP	C-Reactive Protein
CV	Cardiovascular
DBP	Diastolic Blood Pressure
DMC	Data Monitoring Committee
ECG	Electrocardiogram
eCRF	electronic Case Report Form
eGFR	estimated Glomerular Filtration Rate
Electronic Source Data (eSource)	Source data captured initially into a permanent electronic record used for the reconstruction and evaluation of a trial.
Electronic Trial Operations (ETO) System	An electronic system that is used to facilitate the operations of a clinical trial through the collection of study related data. Most common applications of an ETO system within a clinical trial are: subject randomization and product management. Term synonymous with the industry term IVR or IVRS. Note: An individual can interface with an ETO system by using either an IVR or IWR interface. See definitions of IVR and IWR below.
End of Study for individual subject (EOS)	Defined as the last day that protocol specified procedures are conducted for an individual subject
End of Study (primary completion)	Defined as the date when the last subject is assessed or receives an intervention for the purposes of final collection of data for the primary endpoint
Enrollment	Defined as the date the subject is randomly assigned to a treatment group or "randomized"
EPO	Erythropoietin
ESA	Erythropoiesis Stimulating Agent
ET	Early Termination
GCP	Good Clinical Practice
GI	Gastrointestinal
Hb	Hemoglobin
HBV	Hepatitis B Virus

Abbreviation or Term	Definition/Explanation
HCT	Hematocrit
HCV	Hepatitis C Virus
HemoCue	Modified hemoglobin point of care device
HIV	Human Immunodeficiency Virus
HLA	Human Leukocyte Antigen
HTLV	Human T-Lymphotropic Virus
ICF	Informed Consent Form
ICH	International Conference on Harmonisation
IEC	Independent Ethics Committee
Interactive Voice Response (IVR)	Telecommunication technology that is linked to a central computer in real time as an interface to collect and process information.
Interactive Web Response (IWR)	Web based technology that is linked to a central computer in real time as an interface to collect and process information.
IP	Investigational Product
IRB	Institutional Review Board
IV	Intravenous
KDOQI	The National Kidney Foundation Kidney Disease Outcomes Quality Initiative
MACE	Major Adverse Cardiovascular Events
MCH	Mean Corpuscular Hemoglobin
MCHC	Mean Corpuscular Hemoglobin Concentration
MCV	Mean Corpuscular Volume
MedDRA	Medical Dictionary for Regulatory Activities
MI	Myocardial Infarction
MPV	Mean Platelet Volume
ND-CKD	Chronic Kidney Disease Not on Dialysis
PFS	Prefilled Syringe
PIN	Personal Identification Number
POC	Point of Care
PSD	Protocol Specified Dose

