6.4.1 Dosage Adjustments

All dose adjustments will be managed using the IVR/IWR system. In order to maintain the blind, subjects will receive a placebo injection in place of darbepoetin alfa therapy when the dose of study drug is to be withheld per the dosing algorithm, for reasons other than elevated SBP.

The maximum dose of darbepoetin alfa administered at any time during the study will be 300 μ g.

The dose of investigational product may be adjusted based on Hb parameters and SBP values.

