6.4.1.1 Dosage Adjustments Based on Systolic Blood Pressure Values

If the subject's mean SBP is \geq 160 mmHg for **two** consecutive visits (including blood pressure monitoring visits), the dose of investigational product will be withheld.

If the subject's dose is withheld for \leq 2 consecutive dosing visits, the investigational product will be restarted at the subject's previous dose at the dosing visit when the mean SBP is \leq 140 mmHg.

If the subject's dose is withheld for $>$ 2 consecutive dosing visits, the investigational product will be restarted on the initial study dose at the dosing visit when the mean SBP is \leq 140 mmHg.

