7.1.4.2 Additional Visits for Blood Pressure Monitoring

For any subject with a mean SBP \geq 160 mmHg measured during a routine study visit, an additional blood pressure monitoring visit is required 2 weeks later. This visit may be completed within \pm 5 days of the scheduled visit date.

For subjects with mean SBP $<$ 160 mmHg an additional study visit for blood pressure monitoring may also be scheduled 2 weeks after a routine study visit at the discretion of the investigator. This visit may be completed within \pm 5 days of the scheduled visit date.

The procedures and data collected at blood pressure monitoring visits will include:

- Blood pressure and pulse
- Concomitant antihypertensive medications
- Adverse event and serious adverse event assessment

The SBP obtained during these visits will be entered into the IVR/IWR system.

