4.2.19 Receipt of any intravenous (IV) iron therapy

4.2.20 Changes in oral iron therapy

4.2.21 Receipt of ESA therapy

[Page 24, Section 5.1, Screening](#)

Replace:

Subjects who fail screening may be rescreened as described in Section 7.1.2 beginning 28 days after the date of the last screening procedure.

With:

Subjects who fail screening may be rescreened as described in Section 7.1.2 beginning **14** days after the last screening procedure.

[Page 26, Section 6.1, Classification of Products and Medical Devices](#)

Replace:

The medical devices that are provided by Amgen for use in this study include: A modified HemoCue Hb 201+ system hemoglobin analyzer (investigational) and an Omron HEM 705 CP Auto Inflate Blood Pressure Monitor (commercially available).

With:

The medical devices that are provided by Amgen for use in this study include: A modified HemoCue Hb 201+ system hemoglobin analyzer and an **auto inflate** Blood Pressure Monitor.

[Page 27, Section 6.4.1.1, Dosage Adjustments Based on Systolic Blood Pressure Values](#)

Replace:

If the subject's mean SBP is \geq 160 mmHg for three consecutive visits (including blood pressure monitoring visits), the dose of investigational product will be withheld.

With:

If the subject's mean SBP is \geq 160 mmHg for **two** consecutive visits (including blood pressure monitoring visits), the dose of investigational product will be withheld.

[Page 29, Section 6.6, Medical Devices](#)

Replace:

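### The synopsis withholds study drug after three consecutive high blood pressure readings and Section 6.4.1.1 after two, so the current protocol contains two hold rules.

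*Protocol*

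**What the plan says.** The Protocol Synopsis gives the rule for all subjects: "In both dosing groups, the dose of investigational product will be withheld" if "mean SBP is ≥ 160 mmHg for three consecutive visits (including blood pressure monitoring visits". Its restart condition reads "Investigational product will be restarted at the dosing visit when the mean SBP is ≤ 140 mmHg".

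Protocol Section 6.4.1.1, the body section on blood pressure holds, sets the trigger at "160 mmHg for two consecutive visits (including blood pressure monitoring visits), the dose of investigational product will be withheld". It uses the same 140 mmHg restart level and adds what dose follows a hold: the previous dose if no more than two consecutive dosing visits were withheld, the initial study dose if more than two were.

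Three other places bear on how the rule works:

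- Section 7.1.4.2: after a routine visit with mean SBP at or above 160 mmHg, "an additional blood pressure monitoring visit is required 2 weeks later". Below 160 mmHg such a visit is at the investigator's discretion.
- Section 6.4.1: "All dose adjustments will be managed using the IVR/IWR system". The same section excludes blood pressure holds from placebo substitution.
- The SAP states no hold rule. Its Section 1 cites a protocol dated 09 March 2012, which predates Amendment 1 (03 April 2013), whose rationale describes the blood pressure hold.

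**The concern.** The two passages set the same safety rule for the same subjects and differ in the number of readings needed. A site that reads the synopsis and a site that reads Section 6.4.1.1 would expect different decisions for the same patient.

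The rule decides whether a subject with raised blood pressure receives a dose of darbepoetin alfa. Two versions mean that, for some sequences of readings, any decision contradicts one part of the protocol, and it is unclear what counts as a deviation. Cumulative dose and average achieved Hb are both secondary endpoints, and both depend on which doses are given. Because a blood pressure hold is not masked by a placebo injection, site staff can see that a dose was withheld and may find that this disagrees with the synopsis.

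**Working it through.** There is no statistical figure to reproduce. The check compares the passages and traces visit sequences through each rule.

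**1. Are both passages current?** Yes. The synopsis sentence is in the body of the Amendment 3 version, and the synopsis carries other Amendment 3 edits, such as the renamed Hb device. The Amendment 3 log, under "Section 6.4.1.1, Dosage Adjustments Based on Systolic Blood Pressure Values", records three replaced by two in that section. Its synopsis entries contain no matching change. This suggests how the mismatch arose; the finding rests on the two current passages, not on the log.

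**2. What differs?**

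| Element | Synopsis | Section 6.4.1.1 |
|---|---|---|
| SBP level | ≥ 160 mmHg | ≥ 160 mmHg |
| Monitoring visits counted | yes | yes |
| Restart level | ≤ 140 mmHg | ≤ 140 mmHg |
| Consecutive visits needed | 3 | 2 |

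**3. When do the rules disagree?** Take dosing visits at weeks 0 and 4 and a monitoring visit at week 2, with no reading at or above 160 mmHg before week 0. The last two columns give the decision at week 4.

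| Week 0 | Week 2 | Week 4 | Two visits (6.4.1.1) | Three visits (synopsis) |
|---|---|---|---|---|
| ≥ 160 | ≥ 160 | ≥ 160 | withheld | withheld |
| ≥ 160 | ≥ 160 | ≤ 140 | given | given |
| ≥ 160 | ≥ 160 | above 140, below 160 | **withheld** | **given** |
| < 160 | ≥ 160 | ≥ 160 | **withheld** | **given** |
| ≥ 160 | < 160 | any | given | given |
| ≥ 160 | missed | ≥ 160 | **withheld** | **given** |

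- Row 3 (for example 165, 165, 150) assumes that a hold triggered at the monitoring visit carries to the next dosing visit until the restart level is reached.
- Row 4 needs no such assumption: the second high reading falls on the dosing visit itself.
- Row 6 assumes that a missed visit does not break the sequence.

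**4. Can the restart dose differ too?** Extend row 4: weeks 6 and 8 at or above 160, week 12 above 140, week 16 at or below 140. Apply the Section 6.4.1.1 restart-dose rule under either count.

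- Two visits: trigger met at week 4. Weeks 4, 8 and 12 are withheld, which is 3 dosing visits. As 3 > 2, restart is at the initial study dose.
- Three visits: weeks 2, 4 and 6 meet the trigger at week 6. Weeks 8 and 12 are withheld, which is 2 dosing visits. As 2 ≤ 2, restart is at the previous dose.

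In the fixed dose group these two doses are normally the same. In the Hb-based titration group they can differ, so the consequence need not be equal in the two groups.

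**5. Does anything settle the conflict?** Nothing was found. The synopsis refers readers to Sections 4, 7 and 10 for full detail, but not to Section 6 for dosing. No clause says that the body prevails over the synopsis.

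**The case against.** The strongest reply is that sites do not choose the rule. Mean SBP is entered into the IVR/IWR system, and that system assigns the dose, so one programmed rule probably applies to everyone. On this view the synopsis sentence is a leftover from an incomplete amendment, with little effect on the trial. The hold applies to both groups and enters neither the primary endpoint definition nor the sample size calculation. SAP Section 10.6.6 already tabulates doses not administered, with reasons, by visit and treatment group, so holds will be visible in the results. The 165, 165, 150 example also depends on a carry-over that Section 6.4.1.1 does not spell out.

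Much of this stands. Mixed application across sites has not been shown, and no effect on any endpoint can be sized. The carry-over reading follows from counting monitoring visits together with the restart condition, but it is an interpretation.

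It does not remove the conflict. The documents never say which count is programmed, a table of missed doses does not show which rule was meant, and row 4 gives opposite decisions without the carry-over reading.

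**Conclusion.** The concern holds. The current protocol gives two different counts, three and two, for the same blood pressure hold, and identical readings can lead to opposite dosing decisions. With the three readings considered, disagreement is confined to two patterns: high, high, then between the restart and hold levels; and not high, high, high. A missed monitoring visit between two high dosing visits adds a third. When all three readings are at or above 160 mmHg, the rules agree at week 4.

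The documents give no frequency of such readings, so neither the number of subjects affected nor the effect on cumulative dose or Hb can be estimated. The sample size and the planned confidence interval widths do not change. The point must be fixed because a subject-level safety rule is contradictory as written, not because bias in the results has been shown.

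**What to change.** - Have the sponsor's clinical team settle one rule, and make the Synopsis and Section 6.4.1.1 state it identically. This review takes no position on which count is right.
- Confirm that the IVR/IWR specification implements that rule, including whether a hold triggered at a monitoring visit carries to the next dosing visit and how a missed visit is counted. State both points in the text.
- If dosing has begun, list the decisions that would have differed under the other count, and say how they are classified for protocol deviations.

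The cost is about one line of corrected text plus the two clarifications, a specification check and a listing from data the system already holds. As a protocol change it also needs investigator agreement and IEC/IRB approval under Section 12.1, and could travel with the next amendment if timing allows. No extra subjects, visits or procedures are needed.
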